**7.2.10.1 Weekly endpoints**

Additionally, all derived CGM endpoints will be derived on a weekly basis. The following weeks will be analyzed: Baseline (Week), Week 1, Week 2, Week 3, Week 4, Month 3 and Month 6. CGM-Derived parameters will be based on CGM data that fall in the following timeframe:

Week	Time window (Days)	
Baseline	7 days prior to day 1	
Week 1	1	7
Week 2	8	14
Week 3	15	21
Week 4	22	28
Month 3	7 days prior to date of Month 3 visit	
Month 6	7 days prior to date of Month 6 visit	

When deriving weekly endpoints - baseline will be based on the CGM data collected 7 days prior to the date/time of the first CSGI injection. For the AOC endpoint baseline will be the same as for the AOC calculated by day.

**7.2.11 Hypoglycemia Symptom Questionnaire**

This questionnaire measures the severity of 8 symptoms of hypoglycemia on a 1 (absent) to 6 (severe) scale. The symptoms are grouped by type of symptom (Neuroglycopenic or Autonomic) per following table:

Neuroglycopenic Symptoms (Score 1-6)	Autonomic Symptoms (Score 1-6)
Dizziness	Sweating
Blurred vision	Tremor
Difficulty in thinking	Palpitations
Faintness	Feeling of nervousness
Average Neuroglycopenic Symptom Score (ANS)	Average Autonomic Symptom Score (AAS)
Average Total Symptom Score (ATS)	
Overall Assessment of Hypoglycemia	
Do you currently feel hypoglycemic? (Yes/No)	

An average Neuroglycopenic Symptom Score (ANS), Autonomic Symptom Score (AAS) and Average Total Symptom Score (ATS) will be calculated from individual symptom scores. Average will be calculated if at least > 50% items in each group (Neuroglycopenic and Autonomic) will be not missing.

**Overall Assessment of Hypoglycemia**

will be treated as a categorical variable and analyzed with descriptive statistics by timepoints;

## **Gold Scale of Hypoglycemia unawareness**

The questionnaire measures on a 7-point scale a subject's awareness of onset of hypoglycemia by asking a single question "To what extent are you aware of the onset of hypoglycemia?".

Baseline for all questionnaire measures is defined as the last value of obtained just before IV push dose of insulin at visit 3 (Day 1, Baseline).

A separate summary for Average Neuroglycopenic Scores (ANS), Average Autonomic Scores (AAS), Average Total Scores (ATS) and Overall Assessment of Hypoglycemia assessed with PG <70 mg/dl and PG <50 mg/dl will be presented.

### **7.2.12 Local Tolerability**

#### **7.2.12.1 Injection Site Discomfort Assessment**

This assessment consists of a

- Visual Analog Scale (VAS) (0-100mm)
- Delivery Site Discomfort Description and Duration questionnaire that consists of the following questions:
  - Discomfort question with the following categories: Pain, Itching, (Tingling, twitching or numbness), Irritation and Other.
  - Question regarding how long after administration did the discomfort start and how long it lasted.

This assessment is administered at visit 3 (Day 1, Baseline) and Visit 4 (Day 7) with the VAS scale being administered at several timepoints and the discomfort questionnaire being administered at 10 mins following delivery of study drug.

#### **7.2.12.2 Draize Scale**

This scale measures presence/severity of Erythema and Edema Formation on a 0-4 scale (not present-severe) at Visit 4 (Day 7) and visit 7 (Day 28) at multiple timepoints.

## **7.3 Conventions**

### **7.3.1 Technical Requirements**

The statistical analyses will be performed by Quartesian Clinical Research, using SAS Version 9.4 (or higher). Datasets will be prepared using standards from Clinical Data Interchange Consortium (CDISC) Study Data Tabulation Model (SDTM) implementation for human clinical trials and ADaM (Analysis Dataset Model). Tables, figures and listings will be produced in landscape format if not specified otherwise.

### **7.3.2 Summary statistics**

Data will be tabulated by time point where appropriate. The total number of subjects in the study group (N) under the stated population will be displayed in the header of summary tables and figures.

All summaries will be presented by treatment group for baseline and each scheduled visit and timepoint, where applicable. If more than one assessment available per timepoint, then last assessment will be used for analysis.

Summaries will be presented by treatment group and overall. Treatment group labels will be displayed as follows:

CSGI			Placebo	Total
Low Dose (20 ug/hr)	High Dose (80 ug/hr)	Combined (Low + High)		

Listings will be sorted in the following order: subject, parameter, and visit unless otherwise stated. All data will be listed, subjects who were not randomized will be displayed after the randomized treatment/sequence groups.

Continuous variables will be summarized by the number of non-missing observations, mean, median, standard deviation, and minimum and maximum.

Categorical variables will be summarized with frequencies and percentages. For each variable, all pre-specified categories will be shown. Zero counts will be presented without percent.

N will be used as percentage denominator in descriptive summaries, if not specified otherwise.

Missing will be counted as difference of subjects at each visit and number of assessments. Note: Records collected from eCRF or eDT will not be used for 'Missing' statistics and can be used only for reference.

### 7.3.3 Decimal Places

Unless otherwise stated, continuous data will be summarized with the following descriptive statistics: number of non-missing observations (n), arithmetic mean (Mean), standard deviation (SD), median, minimum (Min), maximum (Max). For presentation, Min and Max will have the same number of decimal places as the original data; the mean, geometric mean and median will be presented to 1 decimal place greater than Min, Max; SD will be to 2 decimal places greater than Min, Max; percentages will be presented rounded to 1 decimal place. Number of decimals for descriptive statistics will be limited with 4 decimals. Minimum and maximum will be displayed with the number of decimals reported in CRF and can be limited to 3 decimals; converted or derived values will have from 3 to 4 significant digits in summary statistics and will be determined in case-by-case basis.

If some parameter contains original and calculated values or certain timepoints (e.g. hypoglycemia scores), then one decimal will be added to Min, Max for derived timepoints or parameters, not including other descriptive statistics.

P-values will be displayed with 3 decimal places. P-values that are less than 0.001 will be presented as "<0.001".

## 7.4 Subject Disposition

Subject disposition will be summarized as follows:

- The number of subjects who were screened, screen failures, randomized and who are in each analysis population will be summarized by treatment group and overall.
- The number of early withdrawals and the reasons for withdrawals will be tabulated by treatment group and overall for ITT population

## 7.5 Protocol Deviations

Protocol deviations will be identified during blinded data review by Sponsor and Medical Monitor and classified as major or minor. Subjects with major protocol deviations will be excluded from PP population..

The number of subjects with major and minor protocol deviations will be summarized descriptively with counts and percentages for ITT population and listed.

## 7.6 Demographic and Baseline Characteristics

Demographic characteristics will include:

- Age;
- Gender;
- Ethnicity;
- Race.

Baseline characteristics will include:

- Weight;
- Height;
- Body Mass Index (BMI);
- Body Surface Area (BSA);
- Gold scale for hypoglycemia unawareness;
- Glucose Correction Factor per Unit of Insulin (mg/dL);
- Hemoglobin A1C (%)
- Hemoglobin A1C (%) category ( $\leq 8\%$ ,  $> 8\%$ )
- Duration of diabetes (years)
- Duration of diabetes category ( $< 15$  yrs,  $\geq 15$  yrs)

Demographic and baseline characteristics will be listed and analyzed with descriptive statistics for Safety, ITT and PP population.

## 7.7 Medical History

Subjects will undergo a complete medical history at screening.

Medical history of each subject will be collected at screening visit and coded using the MedDRA 22.0 dictionary.

Medical history will be listed and analyzed with descriptive statistics by SOC and PT for ITT population.

## 7.8 Prior and Concomitant Medications

Subjects should be on a stable dose of all concomitant medications for at least 30 days prior to Screening. All subjects must have their concomitant medications reviewed at each visit. Medications taken within 4 weeks before Day 1 will be documented in the CRF. Any changes to a subject's concomitant medication regimen will be documented.

Prior medication is defined as any medication taken within 4 weeks before treatment administration.

Concomitant medication is defined as any non-study medication taken on or after blinded study treatment was administered.

If dates of medications are incomplete, missing, or medication is ongoing, the medication will be considered as concomitant if there is no evidence that medication intake stopped before study treatment. The medication will be considered as prior if there is an evidence that medication intake started before the study treatment, and there is a possibility that medication intake started not earlier than 6 months before screening.

Concomitant Medications, Drugs/Therapies will be coded using WHODrug Global B3 Mar 2019.

Prior and Concomitant medication will be summarized and listed with ATC level 2 and preferred term for the Safety population.

Patients may have more than one medication per ATC category and PT. At each level of patient summarization, a patient will be counted only once.

## 7.9 Exposure to Study Drug

Extent of exposure (number of days of exposure to study drug) will be presented for the Safety population.

## 7.10 Efficacy Analyses

### 7.10.1 Primary Endpoint

The primary endpoint is the percent change from Induction 1 (baseline visit) to Induction 2 (visit 7, week 4) in plasma epinephrine concentration after 30 minutes of induced hypoglycemia with PG < 50 mg/dL.

Hypotheses of interest:

$H_0: \mu_x = \mu_y$  vs  $H_1: \mu_x \neq \mu_y$

where the treatment comparison of interest (ranked in order of interest) is as follows:

- CSGI Combined vs placebo
- CSGI High vs placebo

- CSGI Low vs placebo
- CSGI High vs CSGI Low

For details regarding multiplicity please see section [7.10.5](#).

### **7.10.2 Primary Efficacy Analysis**

The analysis of the primary endpoint will be performed using a two-group t-test for each treatment comparison of interest. The primary endpoint will also be analyzed, stratifying by duration of diabetes (<15 yrs, ≥15 yrs) as a secondary analysis.

A closed testing hierarchical procedure will be used to control for multiplicity. See section [7.10.5](#).

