#### **6.1.1. Background**

Approximately 20% of the type 1 diabetes mellitus (T1DM) population suffers from recurrent severe hypoglycemia, which is of considerable consequence to the affected persons in rare cases leading to death and to the health care systems as the treatment often involves acute care and even hospitalization.

For many of these people a key component of the underlying pathology is hypoglycemia associated autonomic failure (HAAF). Hypoglycemic events decrease autonomic responsiveness further increasing the risk of subsequent hypoglycemic events thus constituting a vicious cycle. It has been shown scrupulous hypoglycemia avoidance at least partially restores autonomic function and diminishes the risk of hypoglycemia and that this effect lasts for years in some patients.

T1DM patients, with time, lose not only Langerhans' islet B-cell, but also A-cell function leading to glucagon deficiency. As the primary counter regulatory hormone to insulin this increases the risk of hypoglycemia substantially. The risk of HAAF increases as endogenous glucagon is diminished or lost. Administering exogenous glucagon to partially replace the missing endogenous glucagon may therefore, similar to the scrupulous hypoglycemia avoidance, restore autonomic function and diminish the increased hypoglycemia risk.

In support of that hypothesis, continuous subcutaneous administration of low dose glucagon has been shown to decrease the number of nocturnal hypoglycemic events in T1DM (Edelman, ADA annual scientific sessions, 2006).

Glucagon is indicated for the treatment of severe hypoglycemia in a 1 mg dose. Xeris has used its biocompatible, non-aqueous peptide/protein reformulation technology to create a concentrated, low volume, stable glucagon formulation. This glucagon formulation has successfully been delivered using the Omnipod®.

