## 4 ENDPOINTS

### 4.1 Primary Endpoint

Percent change from Induction 1 (baseline visit) to Induction 2 (visit 7, Week 4) in plasma epinephrine concentration after 30 minutes of induced hypoglycemia with PG <50 mg/dL. The average of the non-missing results at each step will be used in analysis.

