### **6 RANDOMIZATION**

The randomization scheme is 1:1:1 for high dose, low dose and placebo. Each group will have 16 subjects, but the placebo group will be matched to high and low infusion rates (8 in each group). The randomization is stratified by site.

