## 10 CHANGES TO PLANNED PROTOCOL ANALYSIS

- Primary analysis endpoint updated to percent change from Induction 1 (baseline visit) to Induction 2 (visit 7, week 4) in plasma epinephrine concentration after 30 minutes of induced hypoglycemia with plasma glucose <50 mg/dL.
- Absolute change from Induction 1 (baseline visit) to Induction 2 (visit 7, week 4) in plasma epinephrine concentration after 30 minutes of induced hypoglycaemia with plasma glucose <50 mg/dL moved from primary to secondary endpoint.
- The primary analyses will also be performed by diabetes duration category (<15 yrs, ≥15 yrs) and included in the secondary analyses.
- The secondary endpoint of describing subject reported severe hypoglycemic events when glucose meter reading <36 mg/dL was updated to glucose meter reading <50mg/dL. This was a typo in the protocol.
- The Per-Protocol Population definition has been updated to include subjects who participate in the study through day 27 with no major protocol deviations because treatment compliance data was not captured for the study.

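### The gate test is an unadjusted t-test on percent change in epinephrine; the plan should prespecify a baseline- and site-adjusted primary model, though the power gain depends on figures the documents do not give

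*SAP*

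**What the plan says.** SAP 4.1 defines the primary endpoint as "Percent change from Induction 1 (baseline visit) to Induction 2 (visit 7, Week 4) in plasma epinephrine concentration" after 30 minutes below 50 mg/dL. Two samples are taken 10 minutes apart at that step (HIS2 in SAP 7.2.9), and "The average of the non-missing results at each step will be used in analysis". SAP 7.10.2 then says: "The analysis of the primary endpoint will be performed using a two-group t-test for each treatment comparison of interest". SAP 7.10.5 puts combined CSGI versus placebo first, so that test gates the other three.

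No baseline covariate, site term, transformation or rank-based backup is named for this endpoint, although SAP section 6 says "The randomization is stratified by site". The three sensitivity analyses in SAP 7.10.3 vary only the handling of missing data. The analysis by diabetes duration does not adjust for baseline epinephrine.

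SAP section 10 discloses the change of scale: "Primary analysis endpoint updated to percent change from Induction 1 (baseline visit) to Induction 2", with absolute change "moved from primary to secondary endpoint".

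**The concern.** Percent change divides by the Induction 1 value. If that value varies widely between subjects, the ratio is right-skewed, its variance grows with the effect, and subjects with small denominators carry much of the mean and the SD. Low baselines are plausible in this population: Protocol 6.1.1 says "Hypoglycemic events decrease autonomic responsiveness", and entry requires a Gold score of at least 4.

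With 16 subjects per arm, a test that leaves out a measured, prognostic baseline can lose power. If the gate fails, no dose comparison can be claimed. A mean of ratios is also hard to read, because it can be well above zero when no typical subject has changed. No planned analysis of the primary endpoint would show whether the result hangs on a few low baselines.

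**Working it through.** **1. The plan's own figure.** SAP section 5 and the protocol synopsis give a difference of 1.5 nmol/L, SD 1.34, alpha 5% and power 80%. So d = 1.5/1.34 = 1.119. The two-sided two-sample t-test needs n = 13.56, hence 14 per group, and 14 x 3 = 42, which matches the synopsis. Power is 81.3% at 14 per group, 86.5% at 16 per group and 94.7% at 32 v 16. All of this is for absolute change. The documents give no effect, SD or power for percent change.

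**2. Behaviour of the ratio.** For lognormal values with CV c and log-scale correlation r between inductions, let s^2 = ln(1 + c^2). With no true change, the expected percent change is 100 x (exp(s^2(1 - r)) - 1).
- c = 0.5, r = 0.8: s^2 = 0.223, giving +4.6%.
- c = 1.1, r = 0.4: s^2 = 0.793, giving +60.9%.

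An invented example: 15 subjects unchanged at 1.5 nmol/L and one moving from 0.15 to 0.6. Mean percent change is 300/16 = +18.75%; mean absolute change is 0.45/16 = +0.028 nmol/L.

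**3. Gate power, multiplicative effect (32 v 16).** Assumed: lognormal values and a log-scale effect of 3.16 x s x sqrt(1 - r^2) x sqrt(1/32 + 1/16), which gives log-ANCOVA about 86% power. No site term; 12,000 simulated trials per row.

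| CV | r | t-test, percent change | percent change + log baseline | log-ANCOVA |
|---|---|---|---|---|
| 0.3 | 0.4 | 70% | 83% | 87% |
| 0.3 | 0.8 | 83% | 86% | 87% |
| 0.5 | 0.6 | 73% | 81% | 86% |
| 0.8 | 0.4 | 54% | 66% | 86% |
| 0.8 | 0.6 | 66% | 74% | 87% |
| 0.8 | 0.8 | 77% | 80% | 86% |
| 1.1 | 0.4 | 44% | 54% | 87% |
| 1.1 | 0.6 | 59% | 66% | 86% |

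Apart from the corner with the highest CV and the lowest correlation, the planned test lies at about 53-83%. Under no effect it rejected in 4.1-5.0% of trials over the full grid.

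**4. Gate power, additive effect (32 v 16).** From SAP section 5: effect 1.5, SD of change 1.34. Assumed: lognormal baseline with mean 1-5 nmol/L and CV 0.3-1.0, values floored at 0.05.
- t-test on percent change: about 57-92%.
- log-ANCOVA: about 78-92%; from about 5 points worse (CV 0.3) to about 31 points better (mean 1, CV 1.0) than the t-test on percent change.
- t-test on absolute change: 93-95%.
- Adding log baseline to the percent-change model: a loss of at most about 2 points, a gain of up to about 12.

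At 16 v 16, log-ANCOVA can be about 9 points worse than the t-test on percent change (for example 74% v 83% at baseline mean 2-3, CV 0.3).

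**5. Cost of the site term.** With seven sites, no true site effect and allocation not balanced within site, log-ANCOVA fell from about 89% to about 84-85% in multiplicative settings. It stayed 4 to 26 points ahead of the percent-change t-test. Stratified allocation should make the loss smaller.

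**The case against.** The strongest objection is that the power comparison depends on the model chosen. Lognormal data with a multiplicative effect is the setting in which log-ANCOVA is the natural analysis. The only effect the documents state is additive, and there log-ANCOVA can lose. This stands: a reader might infer that log-ANCOVA would have far more power, and the documents do not support that, because they give no epinephrine mean, CV or correlation.

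A second inference to avoid is that the log-scale model answers the same question. It shares the null hypothesis of no effect, but it estimates a ratio of geometric means, whereas the t-test compares arithmetic mean percent changes.

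Third, a reader might infer that one low-baseline subject can decide the result. In the example of step 2 the SD in that arm is 75. Against 16 unchanged placebo subjects, t = 18.75/sqrt(75^2/16) = 1.0 on 30 degrees of freedom, p = 0.33. The outlier inflates the SD along with the mean: it can cost significance, but here it does not create it. The positive mean under no change is likewise no bias in the test, since it is common to both arms.

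Fourth, eligibility sets no epinephrine criterion, so low baselines are plausible but not shown. Finally, absolute change, which has no denominator, remains a named secondary endpoint in ITT and PP. That is a partial safeguard, but outside the hierarchy and without baseline adjustment.

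What the objection does not remove is that a prognostic baseline and the stratification factor are in hand and unused in the test that gates everything else.

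**Conclusion.** The concern holds in a limited form. The primary analysis leaves out the baseline value and the site stratum, and it uses a scale that is sensitive to low Induction 1 values. This is a matter of power and interpretability, not of false positives.

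The size is conditional. If effects are multiplicative, the gate loses roughly 4 to 33 points against log-ANCOVA without a site term over most of the assumed range, and more in the worst corner. If the effect is additive as in SAP section 5, the difference runs from about 5 points in favour of the planned test to about 31 against it, and absolute change is the most powerful scale. In the gate settings examined, the t-test on percent change was never the best choice. Baseline adjustment of percent change itself cost almost nothing and sometimes gained a good deal. That is enough to recommend the change, but not to promise a particular gain.

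**What to change.** Before any group-level unblinding for the Week 4 analysis (SAP section 8), rewrite SAP 7.10.2 so that the primary analysis is one linear model with treatment (three levels), log mean HIS2 epinephrine at Visit 3, and site with small sites pooled by a stated rule. Take the four ordered contrasts of SAP 7.10.5 from that model.

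- Preferred response: log mean HIS2 epinephrine at Visit 7. Report each contrast as a geometric mean ratio, expressed as an adjusted percent difference, with 95% CI.
- If the sponsor keeps the arithmetic percent-change estimand: fit the same covariates to percent change and prespecify the log-scale ANCOVA as a named sensitivity analysis.
- Keep the t-tests on absolute and percent change as supportive.

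The change costs SAP wording and one model, with no new data. The downsides are a changed estimand on the log scale, 5-7 degrees of freedom for site with the planned 6-8 centers (fewer after pooling), and a possible small power loss if effects are additive and baseline CV is low. Log values must be positive. SAP 7.2.7 already imputes results below a limit as just under that limit, and percent change would have to divide by the same number.

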### **7.10.3 Sensitivity Analysis**

The following Sensitivity analyses of the primary outcome in the PP population will be conducted:

- All subjects who are lost to follow-up or have missing outcome data will be considered to have a favorable outcome (e.g., value will be set to the largest (maximum) improved change in either treatment groups) in each treatment group
- Subjects who are lost to follow-up or have a missing primary endpoint at Day 27 in the high or low dose group will be considered to have an unfavorable outcome (e.g., value will be set to baseline outcome) whereas in the placebo group will be considered to have a favorable outcome
- Subjects who have a missing outcome data will be excluded from the analysis

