#### 11.1.1. Closed Hierarchical Hypothesis Tests

The analysis of the primary endpoint will be performed using a hierarchical hypothesis test in which an alpha of 5% will be preserved for each test. Testing will be employed in the following order:

- CSGI (combined groups) versus Placebo (if statistically significant <0.05, then the next hypothesis test will be conducted)
- CSGI high dose versus Placebo (if statistically significant <0.05, then the next hypothesis test will be conducted)
- CSGI low dose versus Placebo (if statistically significant <0.05, then the next hypothesis test will be conducted)
- CSGI high dose versus CSGI low dose

Sensitivity analysis of the primary efficacy outcome in the PP population will be conducted where:

- All subjects who are lost to follow-up or have missing outcome data will be considered to have a favorable outcome in each of the treatment groups.
- Subjects who are lost to follow-up or have a missing primary endpoint at Day 27 in the high or low dose group will be considered to have an unfavorable outcome whereas in the placebo group will be considered to have a favorable outcome
- Subjects who have a missing outcome data will be excluded from the analysis

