### **7.1.1 Intent-to-treat Population (ITT or All Randomized)**

The ITT population includes all randomized subjects. The ITT population will be analyzed according to the treatment group to which subjects were randomized.

ITT population will be used for primary and secondary efficacy endpoints.

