### **7.1.2 Per-Protocol Population (PP Population)**

The PP population will be a subset of the ITT population consisting of those subjects who:

- Satisfy all of the inclusion/exclusion criteria;
- Participate in the study through day 27 with no major protocol deviations

All protocol deviations will be assessed and documented on a case-by-case basis before the database lock, and deviations considered to have a serious impact on the efficacy results will lead to the relevant subject being excluded from the PP population. Before database lock, potential subject exclusions from PP population will be reviewed by the Sponsor and documented in a subject evaluability document.

PP population will be used for sensitivity analysis of the primary efficacy endpoint.

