## 12 LIST OF TABLES, FIGURES AND LISTINGS

The following table includes details of the tables, figures and listings (TFLs) for the study. Those marked with an asterisk (\*) are planned for the primary endpoint analysis and presentation of the accompanying safety analysis for that time period (See Section 8).

Table Number	Table Title	Shell Number (if repeat)
14.1.1.1*	Summary of Subject Disposition - All Subjects	
14.1.1.2*	Summary of Analysis Populations - All Randomized Subjects	
14.1.2*	Summary of Protocol Deviations - Intent-to-Treat Population	
14.1.3.1*	Summary of Demographic and Baseline Characteristics - Safety Population	
14.1.3.2*	Summary of Demographic and Baseline Characteristics - Intent-to-Treat Population	14.1.3.1
14.1.3.3*	Summary of Demographic and Baseline Characteristics - Per Protocol Population	14.1.3.1
14.1.4*	Summary of Medical History - Intent-to-Treat Population	
14.2.1.1*	Percent change from Induction 1 (Baseline visit) to Induction 2 (Visit 7, Week 4) in Plasma Epinephrine Concentration During Induced Hypoglycemia with PG <50 mg/dl Intent-to-Treat Population	
14.2.1.2*	Percent change from Induction 1 (Baseline visit) to Induction 2 (Visit 7, Week 4) in Plasma Epinephrine Concentration During Induced Hypoglycemia with PG <50 mg/dl Per Protocol Population	14.2.1.1
14.2.1.3*	Percent change from Induction 1 (Baseline visit) to Induction 2 (Visit 7, Week 4) in Plasma Epinephrine Concentration During Induced Hypoglycemia with PG <50 mg/dl, Sensitivity analysis 1* Per Protocol Population	14.2.1.1
14.2.1.4*	Percent change from Induction 1 (Baseline visit) to Induction 2 (Visit 7, Week 4) in Plasma Epinephrine Concentration During Induced Hypoglycemia with PG <50 mg/dl, Sensitivity analysis 2* Per Protocol Population	14.2.1.1
14.2.1.5*	Percent change from Induction 1 (Baseline visit) to Induction 2 (Visit 7, Week 4) in Plasma Epinephrine Concentration During Induced Hypoglycemia with PG <50 mg/dl, Sensitivity analysis 3* Per Protocol Population	14.2.1.1
14.2.2.1.1*	Absolute change from Induction 1 (Baseline visit) to Induction 2 (Visit 7, Week 4) in Plasma Epinephrine Concentration During Induced Hypoglycemia with PG <50 mg/dl Intent-to-Treat Population	14.2.1.1

Table Number	Table Title	Shell Number (if repeat)

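### The rules for subjects lost to follow-up are applied in the Per-Protocol population, which has already excluded almost all of them, so the effect of dropout on the ITT primary result is not tested

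*SAP*

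**What the plan says.** The primary endpoint is "Percent change from Induction 1 (baseline visit) to Induction 2 (visit 7, Week 4) in plasma epinephrine concentration" after 30 minutes of hypoglycemia (SAP 4.1). On the population, SAP 7.1.1 says "ITT population will be used for primary and secondary efficacy endpoints". On the method, SAP 7.10.2 says "The analysis of the primary endpoint will be performed using a two-group t-test for each treatment comparison of interest". Neither section says what happens to a randomised subject with no Week 4 value.

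Missing outcomes are addressed only in SAP 7.10.3, which opens: "The following Sensitivity analyses of the primary outcome in the PP population will be conducted". Its three rules are:

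- **Rule 1:** every missing outcome, in any arm, is set to the largest improvement observed.
- **Rule 2:** "Subjects who are lost to follow-up or have a missing primary endpoint at Day 27 in the high or low dose group" are given an unfavourable value (no change from baseline); the corresponding placebo subjects are given a favourable one, which is not defined.
- **Rule 3:** subjects with a missing outcome are left out.

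PP membership requires that subjects "Participate in the study through day 27 with no major protocol deviations" (SAP 7.1.2).

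The PP restriction is not a single slip. Protocol 11.1.1 has it too ("Sensitivity analysis of the primary efficacy outcome in the PP population will be conducted where"), and the protocol's own PP definition, at least 90% of treatment through Day 27, also removes early losses. In SAP section 12, Tables 14.2.1.3 to 14.2.1.5 are all PP tables; the last is titled "Sensitivity analysis 3* Per Protocol Population". SAP section 10 revises the PP definition but leaves the population for these analyses unchanged.

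**The concern.** The rules are written for people who leave, but they are run in a set defined by people having stayed. A subject lost before day 27 is not in PP. A subject lost after Visit 7 (Day 28±1) already has the primary value. The lost-to-follow-up part of rules 1 and 2 therefore has almost nobody to act on.

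What is at stake is the robustness check, not the primary test. Withdrawals and their reasons are tabulated by arm in ITT (SAP 7.4), so uneven dropout would be seen, but its effect on the estimate would not be quantified. Three PP sensitivity tables could then be cited as evidence of robustness to dropout that they do not provide.

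**Working it through.** **1. Who each rule can reach**

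| Subject | In ITT? | In PP? | Imputed by rules 1 and 2 as planned? |
|---|---|---|---|
| Lost before day 27 | Yes | No | No |
| Reaches day 27, no usable Week 4 epinephrine | Yes | Yes, unless judged a major deviation | Yes |
| Lost after Visit 7 | Yes | Yes, if otherwise eligible | Not needed; value exists |

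Rule 3 in PP (Table 14.2.1.5) appears to repeat the plain PP analysis (Table 14.2.1.2), since a t-test already omits missing values. Comparing the ITT and PP tables does not isolate dropout either: both rest on observed values, and PP also removes major deviators.

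**2. The plan's own attrition allowance**

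Inputs: difference 1.5 nmol/l, SD 1.34 nmol/l, two-sided alpha 5%, power 80% (protocol synopsis; SAP 5 and 7.10.1). The standardised difference is 1.5/1.34 = 1.119. The two-sample t calculation gives 13.56, rounded up to 14 per group; 3 × 14 = 42, which matches the synopsis. Randomising 48 allows for 48 − 42 = 6 losses (6/48 = 12.5%), or two per arm if even.

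**3. What the rules would do in ITT**

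This is an illustration on the absolute-change scale, because the documents give no effect or SD for percent change. Assumptions: 32 active subjects with mean 1.5, 16 placebo with mean 0, SD 1.34, losses at random. Unfavourable means zero change; favourable means the maximum M observed over all arms, or alternatively the placebo maximum.

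With *a* active and *p* placebo subjects lost, the expected differences are:

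- Complete cases: 1.5
- Rule 2: 1.5 × (32 − a)/32 − (p/16) × M
- Rule 1, with the same fraction f lost in each arm: 1.5 × (1 − f), because M cancels

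For two losses per arm (a = 4, p = 2), the expected all-arm maximum is about 4.21 and the expected placebo maximum about 2.28:

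- Rule 2, all-arm maximum: 1.5 × 28/32 − (2/16) × 4.21 = 1.3125 − 0.526 = 0.79
- Rule 2, placebo maximum: 1.3125 − (2/16) × 2.28 = 1.03
- Rule 1: 1.5 × 14/16 = 1.31

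The share of trials significant in favour of CSGI (two-sided pooled t-test at 0.05) comes from simulation, 20,000 runs per scenario:

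| Losses per arm | Complete cases | Rule 1 | Rule 2, all-arm max | Rule 2, placebo max |
|---|---|---|---|---|
| 1 | 1.50 (93%) | 1.41 (87%) | 1.14 (74%) | 1.26 (84%) |
| 2 | 1.50 (92%) | 1.31 (77%) | 0.79 (33%) | 1.03 (66%) |
| 3 | 1.50 (89%) | 1.22 (64%) | 0.44 (6%) | 0.80 (45%) |

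With no losses the result is 1.50 (95%). For six losses split unevenly, rule 2 with the all-arm maximum gives:

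| Active/placebo lost | 2/4 | 3/3 | 4/2 | 5/1 | 6/0 |
|---|---|---|---|---|---|
| Difference (significant) | 0.34 (3%) | 0.57 (12%) | 0.79 (33%) | 1.00 (61%) | 1.22 (84%) |

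**4. What rule 2 gives as planned, in PP**

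After 4 active and 2 placebo subjects are lost before day 27, PP holds at most 28 and 14.

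- No further missing value: 1.50 (92%). The six early losses have no effect on the result.
- One active PP value missing: 1.5 × 27/28 = 1.45 (90%)
- One placebo PP value missing: 1.5 − (1/14) × 4.21 = 1.20 (71%)
- One of each: 1.45 − 0.30 = 1.15 (67%)

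**The case against.** Five points can be made on the other side.

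- **The rules are not wholly empty in PP.** They also cover missing outcomes, and the clamp has several points of failure: rescheduling for out-of-range glucose, a 120-minute limit on baseline stabilisation, and a restart if glucose rises above 54 mg/dL. Deviations are judged case by case, so such subjects may stay in PP and be imputed. This stands: the documents do not show whether dropout or failed sampling would be the main source of missing data. It does not help with subjects who leave before day 27.
- **The figures show no harm to the primary result.** Losses are simulated at random, so the complete-case difference stays at 1.50 throughout, and the low percentages come from extreme imputation. This is correct, and they should be read only as bounds.
- **The scale is not that of the primary endpoint.** Absolute change is now secondary. This also stands: the size on the percent-change scale is unknown.
- **Extreme single imputation is a blunt tool with 16 per arm.** True, but these are the sponsor's own rules. The point is that they are run where they cannot work, not that they are the best method.
- **The impact is limited.** This is a phase 2a trial, supportive analyses are descriptive, subject-level listings are planned, and further analyses are allowed in the study report. ITT bounds could therefore be computed later. What would be missing is pre-specification, which matters because the population and the imputed value could then be chosen after group results are known.

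**Conclusion.** The concern holds. A stated rule fails its own purpose: as planned, no subject lost before day 27 can be imputed, and no planned analysis measures what their absence does to the ITT result. This should be fixed, but it does not invalidate the primary test, its alpha or the data.

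Under the illustrative assumptions, at the plan's own allowance of six losses split evenly, applying rule 2 in ITT moves the combined-dose difference from 1.50 to 0.79 nmol/l. The choice between the two readings of favourable for placebo alone moves the chance of significance from 33% to 66%, so that value needs defining. These figures rest on the absolute scale, random losses and an assumed number and split of losses. That the rules miss early dropouts rests only on the definitions in the documents.

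**What to change.** Before any group-level unblinding of the primary endpoint (SAP section 8):

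1. In SAP 7.10.3 and Tables 14.2.1.3 and 14.2.1.4, run rules 1 and 2 in the ITT population.
2. Drop rule 3 and Table 14.2.1.5. Moving it to ITT would only duplicate Table 14.2.1.1.
3. Keep Table 14.2.1.2 as the PP analysis.
4. In rule 2, say which value is favourable for placebo: the largest percent change in any arm, as in rule 1, or the largest in placebo.
5. In SAP 7.10.2, state that the primary ITT t-test uses subjects with non-missing Induction 1 and Induction 2 values.
6. Record the change in SAP section 10, since protocol 11.1.1 also specifies PP.
7. Present rules 1 and 2 as bounds.

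The cost is edits to three SAP sections and the three sensitivity-table entries, with no new data. There are two drawbacks. The extreme-case results may look less favourable. On the percent-change scale, a single maximum could also be set by one subject with a low baseline value, which is a further reason to label the results as bounds.
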